5.9 Covariates

No adjustments for covariates are planned in the analyses.

5.10 Timing of Analyses

The primary analysis will be conducted when all treated subjects in a cohort have been followed for at least 6 months or come off study, whichever comes first. Subsequent data cutoff dates may be defined to allow for more precise estimates of time-to-event endpoints.

Interim analysis for futility will be performed separately for each cohort after at least 12 subjects of a given cohort have been treated and are efficacy evaluable post-baseline.

6 PLANNED ANALYSES

6.1 Disposition

Patient disposition will be summarized by cohort and total for all enrolled patients with descriptive statistics. Patients who discontinue study treatment and patients who discontinue the study will be summarized along with reason for discontinuation. The number of patients who signed informed consent and the number and percentage of patients in each analysis set will be summarized.

6.2 Demographic and Baseline Characteristics

Demographics and baseline characteristics, including age at consent, gender, ethnicity, race, baseline height, weight, and ECOG score will be listed and summarized by cohort and total using the FAS. Disease specific characteristics will be listed and summarized by cohort and total using the FAS.

6.3 Protocol Deviations

Important protocol deviations (defined as protocol violations by Seattle Genetics) are those that represent a divergence from the protocol that could have a significant effect on the integrity of the study data, or on the subject's rights, safety, or welfare. Important protocol deviations also include exemptions to the study inclusion/exclusion criteria and will be summarized by category. A list of patients with important protocol deviations will be presented.

6.4 Treatment Administration

Treatment administration will be summarized with descriptive statistics using the safety analysis set. Summaries may include but are not limited to the following:

- Duration of treatment (in weeks), which is defined as time from the first study dose to the earliest of 21 days after the last study dose, EOT visit, death date or start date of subsequent anticancer therapy if applicable.
- Number of cycles per patient

- Number and percentage of patients who were treated at each cycle
- Cumulative doses, which is defined as sum of the actual dose across all cycles.
- Average dose per cycle
- Absolute dose intensity (ADI), which is defined as the actual dose in mg/kg per week that a patient received over the entire treatment period. That is, $ADI = \frac{\text{Cumulative doses}}{\text{treatment period in weeks}}$, where treatment period is defined as time from the first study dose to 21 days after the last study dose $[(\text{last dose date} + 21) - \text{first dose date}] / 7$ regardless of death date.
- Relative dose intensity (RDI), which is defined as the ADI divided by the intended dose intensity (IDI). That is, $RDI = \frac{ADI}{IDI} \times 100$, where IDI is defined as the intended dose (i.e., 2 mg/kg regardless of dose reduction in later cycles) in mg/kg per week.
- Number and percentage of patients whose dose was ever modified, which will be summarized by modification type (delay, reduction, unplanned dose adjustment), cycle and overall (i.e., overall drug administrations for a patient). The number and percentage of doses that were modified may also be summarized.

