5.2.3. Dose and Administration

LV is administered by IV infusion given over approximately 30 minutes. LV must not be administered as an IV push or bolus. In the absence of infusion-related reactions (IRR), the infusion rate for all subjects should be calculated in order to achieve a 30-minute infusion period.

However, given the variability of infusion pumps from site to site, a window between -5 minutes and +10 minutes is permitted (i.e., infusion time is 30 minutes -5 min/+10 min).

LV can be administered via central venous access line (preferred) or peripheral IV. Clinical site staff should monitor the infusion site closely for redness, swelling, pain, and infection during and at any time after administration. Advise subjects to report redness or discomfort promptly at the time of administration or after infusion. The IV bag containing LV should not be mixed with other medications.

Dosing is based on the subject's actual body weight at the beginning of each cycle.

Detailed instructions for dose preparation are provided in the Pharmacy Instructions.

Part A (q3wk dosing): LV at a dose of 2.5 mg/kg (maximum dose of 250 mg per infusion) will be administered on Day 1 of each 21-day cycle by IV infusion given over approximately 30 minutes. **For subjects weighing greater than 100 kg, dose calculations will be based on 100 kg for these individuals (including dose reductions).** Rounding is permissible within 1 mg of nominal dose. Any subject receiving >200 mg LV per infusion (weight >80 kg) is required to receive prophylactic G-CSF.

Part B (q1wk dosing): LV at a dose of 1.0 or 1.25 mg/kg will be administered on Day 1, Day 8, and Day 15 of each 21-day cycle. The maximum dose will be 200 mg per infusion.

Part C (2q3wk or q1wk dosing): LV at a dose of 1.5 mg/kg will be administered on Day 1 and Day 8 but not Day 15 of each 21-day cycle (2q3wk) for Arm 1 and Arm 2. LV at a dose of 1.25 mg/kg will be administered on Day 1, Day 8, and Day 15 of each 21-day cycle (q1wk) for Arm 3. The maximum dose of LV for all 3 arms will be 200 mg per infusion. For Arm 2 and Arm 3, pembrolizumab infusion must start approximately 60–90 minutes after administration of LV (see Section 5.3.3).

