3 STUDY DESIGN

This global, open-label, multicenter trial is designed to assess the activity, safety, and tolerability of LV monotherapy for the treatment of solid tumors. Subjects with the following advanced solid tumors will be enrolled:

Cohort 1: SCLC

Cohort 2: NSCLC-squamous

Cohort 3: NSCLC-nonsquamous

Cohort 4: HNSCC

Cohort 5: esophageal squamous cell carcinoma (esophageal-squamous)

Cohort 6: gastric and gastroesophageal junction (GEJ) adenocarcinoma

Interim futility analyses will be performed separately for each cohort after at least 12 subjects of a given cohort have been treated and are efficacy evaluable post-baseline (Error! Reference source not found.). Enrollment to each cohort may be held after 12 subjects for interim futility analysis of the respective cohorts. The Bayesian predictive probability approach will be used to determine the futility criteria. At the time of each interim analysis, the predictive probability of success (PPoS) will be calculated. A PPoS <10% indicates that it is unlikely the objective response rate (ORR) will be better than the response rate of current standard of care at the end of the study given the interim result. Based on efficacy and safety data, together with the PPoS, a cohort may be stopped early by the sponsor.

In all subjects, LV will be administered by IV infusion at a dose of 2.5 mg/kg on Day 1 of each 21-day cycle. Dosing may not exceed 250 mg per infusion. An individual's dose may be modified based upon treatment-related adverse events (AEs). Tumor assessment according to Response Evaluation Criteria in Solid Tumors version 1.1 (RECIST v1.1) will be performed every 6 weeks for the first 12 months and then every 12 weeks thereafter. Objective responses will be confirmed with repeat scans 4-6 weeks after the first documentation of response.

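### The relative dose intensity formula ignores the 250 mg cap, so on measured weight a fully compliant Part A subject above 100 kg scores lower by the factor 100/weight; its 2 mg/kg intended dose also conflicts with the planned 2.5 mg/kg.

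*SAP*

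**What the plan says.** SAP 6.4 builds RDI from three definitions.

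- Cumulative dose: "Cumulative doses, which is defined as sum of the actual dose across all cycles". The weight used to express it per kg is not given.
- Absolute dose intensity (ADI), "which is defined as the actual dose in mg/kg per week that a patient received over the entire treatment period": cumulative dose over the treatment period in weeks, "where treatment period is defined as time from the first study dose to 21 days after the last study dose".
- Intended dose intensity (IDI), the denominator: "where IDI is defined as the intended dose (i.e., 2 mg/kg regardless of dose reduction in later cycles) in mg/kg per week".

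RDI is 100 × ADI/IDI.

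On the planned dose, SAP 3 says "LV will be administered by IV infusion at a dose of 2.5 mg/kg on Day 1 of each 21-day cycle" and adds "Dosing may not exceed 250 mg per infusion". Protocol 5.2.3 gives the same Part A dose and cap. It bases dosing on actual body weight at the start of each cycle, but above 100 kg "dose calculations will be based on 100 kg for these individuals (including dose reductions" are covered too. Protocol 5.2.4.1 and Table 9 accordingly cap the reduced levels of 2.0 and 1.5 mg/kg at 200 and 150 mg.

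Protocol 9.3.8.1 promises a dose intensity summary and leaves the details to the SAP, so SAP 6.4 is the only definition. The SAP covers the original protocol, which had the every-3-week schedule only.

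**The concern.** The dose a subject can receive is capped in mg, but the dose the subject is compared with is a fixed mg/kg figure. Above 100 kg the mg/kg received falls as weight rises while the denominator stays put, so a subject with no delay, omission or reduction loses RDI purely through weight. RDI is meant to show how much of the planned treatment was delivered. It should not mix a limit required by the protocol with dose lost through delays and reductions.

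The same bullet raises a second question. Its intended dose of 2 mg/kg is not the 2.5 mg/kg of SAP 3 and protocol 5.1 and 5.2.3; it equals dose level -1 in protocol Table 9. That affects subjects of every weight.

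**Working it through.** **Inputs.** Planned dose 2.5 mg/kg every 21 days and cap 250 mg (SAP 3; protocol 5.2.3). Intended dose in the RDI formula 2 mg/kg (SAP 6.4). Treatment period [(last dose + 21) − first dose]/7 weeks (SAP 6.4).

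**Set-up.** Take a Part A subject with six full doses on time; the number of cycles cancels. The period is (5 × 21 + 21)/7 = 18 weeks. Dose per infusion is min(2.5 × weight, 250) mg. SAP 6.4 asks for mg/kg per week without saying whether the 2 mg/kg is first divided by three weeks. The main reading here is per 21-day cycle, so IDI = 2/3 = 0.667 mg/kg per week.

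**At 100 kg.** 250/100 = 2.5 mg/kg per infusion. ADI = 6 × 2.5/18 = 0.833. RDI = 0.833/0.667 = 125.0%. With an intended dose of 2.5 mg/kg, RDI = 0.833/0.833 = 100.0%.

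**At 120 kg, measured weight.** 250/120 = 2.083 mg/kg per infusion. ADI = 6 × 2.083/18 = 0.694. RDI = 0.694/0.667 = 104.2%, or 0.694/0.833 = 83.3% with 2.5 mg/kg.

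**Fully compliant subject, measured weight:**

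| Weight (kg) | mg/kg received | RDI, 2 mg/kg per cycle | RDI, 2.5 mg/kg per cycle |
|---|---|---|---|
| up to 100 | 2.500 | 125.0% | 100.0% |
| 110 | 2.273 | 113.6% | 90.9% |
| 120 | 2.083 | 104.2% | 83.3% |
| 125 | 2.000 | 100.0% | 80.0% |
| 130 | 1.923 | 96.2% | 76.9% |
| 140 | 1.786 | 89.3% | 71.4% |

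In both RDI columns the ratio to a compliant subject at or below 100 kg is 100/weight, for example 104.2/125.0 = 83.3/100.0 = 0.833. Because the caps at 2.0 and 1.5 mg/kg are also reached at 100 kg, the factor is the same at the reduced levels.

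**What this hides.** Over six cycles the compliant 120 kg subject accumulates 6 × 2.083 = 12.5 mg/kg. A subject at or below 100 kg who drops to 2.0 mg/kg from cycle 2 accumulates 2.5 + 5 × 2.0 = 12.5 mg/kg. Their RDI is identical.

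**Which weight.** If mg/kg is taken on the 100 kg dosing weight, 250 mg is 2.5 mg/kg at every weight above 100 kg. RDI is then flat: 125% with 2 mg/kg, 100% with 2.5 mg/kg.

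**The 2 versus 2.5 mg/kg conflict.** The two figures change every Part A RDI by 2.5/2 = 1.25. With 2 mg/kg in the denominator, a subject treated at 2.0 mg/kg throughout would score 100%.

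**Time unit.** Read literally as 2 mg/kg per week, IDI gives 0.833/2 = 41.7% for every compliant subject up to 100 kg and 0.694/2 = 34.7% at 120 kg. The low level there comes from the time unit, not the cap.

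**How many subjects.** The documents give no weights. Assuming normal weights with mean 75 kg and SD 16 kg, or mean 80 kg and SD 18 kg, 6.0% or 13.4% exceed 100 kg. That is about 4 to 10 of the maximum 72 in Part A. The average of min(1, 100/weight) is 0.996 or 0.989, so on a 100% baseline the Part A mean falls by 0.4 to 1.1 points. Among those above 100 kg it is 0.938 or 0.921, a fall of about 6 to 8 points.

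**The case against.** A reader might infer that a compliant subject at the weight cap is reported as under-dosed. The documents do not support that. At exactly 100 kg the full 2.5 mg/kg is given, and with the 2 mg/kg that SAP 6.4 actually writes, read per cycle, that subject scores 125%. RDI falls below 100% only above 250/2 = 125 kg. The 91%, 83%, 77% and 71% at 110 to 140 kg need a 2.5 mg/kg denominator that the RDI bullet does not contain. What stands is the relative loss of 100/weight under either figure.

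It is also fair to say that SAP 6.4 does not fix the weight, and that a programmer following protocol 5.2.3 could use 100 kg and remove the effect. This makes the cap problem conditional. It does not settle it, because dose received in mg/kg is most naturally read on measured weight.

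A further tempting step is that the cap would be mistaken for toxicity-driven dose loss in a group already known to tolerate treatment poorly. That goes too far. SAP 6.4 tabulates modifications by type, SAP 6.6.1 summarises adverse events leading to delay or reduction, and SAP 6.2 lists baseline weight, so a capped compliant subject can be recognised. The 5 of 11 subjects with neutropenia-associated serious events in protocol 3.2.2 come from the phase 1 breast cancer study and from doses above 200 mg, which at 2.5 mg/kg means above 80 kg. They are not Part A subjects above 100 kg.

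Finally, the effect on the cohort mean is small, and 72 is a ceiling because sites left Part A when Amendment 1 was activated. Both points hold and limit the severity.

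**Conclusion.** The point holds in a limited form. The SAP 6.4 denominator has no cap term; if ADI uses measured weight, compliant Part A subjects above 100 kg lose RDI in proportion to weight, for example one sixth at 120 kg. The larger effect in the same bullet is the conflict between 2 and 2.5 mg/kg, which moves every Part A value by a factor of 1.25 and at present partly masks the cap effect. Replacing only that number would still leave compliant heavy subjects below 100%.

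The conclusion rests on measured weight in ADI and an intended dose per 21-day cycle, neither of which the SAP states. The number of subjects affected cannot be known from the documents; the 6% to 13% and the 0.4 to 1.1 points are assumption-based. Parts B and C lie outside this SAP. If the formula were carried over, their 200 mg cap would bind only above 200/1.0 = 200 kg, 200/1.25 = 160 kg or 200/1.5 = 133 kg.

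RDI is descriptive. No efficacy endpoint and no futility rule uses it, so this is a desirable correction rather than an essential one.

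**What to change.** In SAP 6.4:

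1. Reconcile the intended dose with SAP 3 and protocol 5.1 and 5.2.3, so that one planned mg/kg figure is used throughout.
2. Define RDI as total mg received over total mg intended, with intended mg per infusion = min(reconciled planned mg/kg × weight at cycle start, protocol cap in mg). Accrue the intended total over the treatment period already defined, so that delays still count. Alternatively, keep mg/kg but use the capped dosing weight in both numerator and denominator.
3. State the time unit of IDI (per week, converted from a 21-day cycle) and the weight used for ADI.

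With the cap in the denominator and a planned dose that matches the one administered, a fully compliant subject scores 100% at every weight. The cost is SAP wording and a small programming change. Weight is measured on Day 1 of each cycle (protocol 6.2.3.1) and administration is recorded in the case report form (protocol 5.7), so no new data are needed.

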3.2.5. Rationale for Selection of 2q3wk LV Dose (Part C)

LV monotherapy has been extensively evaluated across a range of doses and schedules in subjects with mBC in the concurrently ongoing phase 1 study SGNLVA-001 (see Section 1.2.4.3). In Part E of this study, 81 patients with mBC received LV administered at 1.0, 1.25, or 1.5 mg/kg weekly (q1wk). No DLTs were observed at any of the 3 starting doses evaluated in the dose escalation phase (Seagen Inc., data on file).

Preliminary efficacy results from Part E of the SGNLVA-001 study are shown in Figure 1 in Section 1.2.4.4 (data cut 06-Jan-2021). There appears to be greater magnitude of tumor size reduction with increasing dose of LV q1wk with the 1.5 mg/kg dose having the highest proportion of patients with measurable response. However, the frequency of AEs generally appears to increase with increasing dose as well. Table 2 in Section 1.2.4.3 summarizes the most commonly reported AEs by dose in SGNLVA-001 (26-July-2021, Seagen Inc., data on file). Due to the high frequency of neutropenia at the LV 1.5 mg/kg q1wk dose, (67% of patients with 44% of patients having Grade ≥ 3), accrual to this expansion cohort was paused. Although higher efficacy had been observed with the 1.5 mg/kg dose level, the better safety and tolerability of the 1.25 mg/kg dose led to further expansion of this cohort.

In the patients treated with LV monotherapy at the 1.25 mg/kg q1wk dose level, the relative dose intensity started to decrease by Cycle 2 (C2) leading to 2 doses being administered in every 3-week cycle. Similarly, most of the clinically significant neutropenia events in the 1.5 mg/kg dose level occurred after 3 weekly doses. Overall, these observations suggested that an LV drug holiday may be needed to mitigate AEs, including neutropenia, for long-term treatment. This is further supported by PK simulation which demonstrated that giving LV 1.5 mg/kg on Days 1 and 8 every 21 days (2q3wk) would result in similar PK exposures as 1.25 mg/kg q1wk dosing schedule. Based on this rationale, the intermittent dosing schedule of LV 1.5 mg/kg 2q3wk is being explored as monotherapy in Part F of study SGNLVA-001.

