9.3.8.1. Extent of Exposure

Duration of treatment, number of cycles, total dose, and dose intensity will be summarized. Dose modifications, including dose delay, dose reduction, and unplanned dose adjustment, will be summarized. Details will be provided in the SAP.

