1 INTRODUCTION

This document outlines the statistical methods to be implemented within the scope of Protocol SGNLVA-005, entitled “Open-Label Phase 2 Study of Ladiratuzumab Vedotin (LV) for Unresectable Locally Advanced or Metastatic Solid Tumors”, Original version dated 22Apr2019. Results of the proposed analyses will become the basis of the clinical study report for this protocol.

The purpose of this plan is to provide specific guidelines from which the analysis will proceed. All planned analyses specified in this document will be performed. Any changes to this plan, in the form of “post hoc” or “data driven” analyses will be identified as such in the final clinical study report (CSR). Any changes will either be reflected in amendments to this plan before the database lock or specifically documented in the CSR.

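### The SAP's dose-intensity period, not updated for Parts B and C, understates absolute dose intensity under q1wk and 2q3wk dosing

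*SAP*

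**What the plan says.** SAP 6.4 (Treatment Administration) defines ADI as "the actual dose in mg/kg per week that a patient received over the entire treatment period". The divisor is [(last dose date + 21) − first dose date]/7, described as "where treatment period is defined as time from the first study dose to 21 days after the last study dose", and it is applied whatever the date of death. RDI is ADI over the intended dose intensity (IDI) × 100, "where IDI is defined as the intended dose (i.e., 2 mg/kg regardless of dose reduction in later cycles) in mg/kg per week". Duration of treatment also uses last dose + 21 days, but only as one of four candidate end dates. The earliest of that date, the EOT visit, death and new anticancer therapy applies.

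The SAP states that it serves the protocol's "Original version dated 22Apr2019" (SAP 1). SAP 3 describes a single schedule: "In all subjects, LV will be administered by IV infusion at a dose of 2.5 mg/kg on Day 1 of each 21-day cycle".

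Protocol Amendment 04 has two further schedules. In Part B (Protocol 5.2.3), "LV at a dose of 1.0 or 1.25 mg/kg will be administered on Day 1, Day 8, and Day 15 of each 21-day cycle". Part C Arm 3 uses the same three days (q1wk), and Part C Arms 1 and 2 dose on Days 1 and 8 only (2q3wk). Protocol 9.3.8.1 keeps the summary ("Duration of treatment, number of cycles, total dose, and dose intensity will be summarized") and leaves the details to the SAP. The SAP contains no other rule.

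**The concern.** A 21-day tail closes the last cycle only if the last dose falls on Day 1. If it falls on Day 15 (q1wk) or Day 8 (2q3wk), the tail runs 14 or 7 days past the end of the cycle, into time when no dose was planned. A subject who received every dose on time then looks under-dosed, and by more under q1wk.

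Most planned subjects are on these schedules: up to 252 in Part B plus about 90 in Part C is 342 of about 414, or 83% (Protocol 9.1). Dose intensity also has a role in the design. Protocol 3.2.5 supports 2q3wk partly by noting that, on 1.25 mg/kg q1wk, "the relative dose intensity started to decrease by Cycle 2 (C2) leading to 2 doses being administered in every 3-week cycle". Part C Arms 2 and 3 then set 2q3wk and q1wk side by side, each with pembrolizumab. A summary that lowers q1wk more than 2q3wk at equal compliance could mislead a reader on that question.

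**Working it through.** **Inputs.** Dosing days: Day 1 (q3wk), Days 1 and 8 (2q3wk), Days 1, 8 and 15 (q1wk), from Protocol 5.2.3. Cycle length: 21 days. Period formula and IDI: SAP 6.4. Assumption: k full cycles, every dose on time, and the last dose is the last planned dose of its cycle.

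**Figure in the plan.** Neither document gives an ADI or RDI result. Protocol Table 8 gives the planned q1wk dose per cycle, and it reproduces: 3 × 1.0 = 3.0 and 3 × 1.25 = 3.75 mg/kg. Planned intensity per week is therefore 3.0/3 = 1.0 and 3.75/3 = 1.25 mg/kg for q1wk, and 2 × 1.5/3 = 1.0 mg/kg for 2q3wk.

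**Period under the SAP formula.** Days from first to last dose are 21(k−1) for q3wk, 21(k−1)+7 for 2q3wk and 21(k−1)+14 for q1wk. Adding 21 and dividing by 7 gives 3k, 3k+1 and 3k+2 weeks. The true length is 3k weeks.

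**Effect on ADI.** ADI is multiplied by true period over SAP period: 1 for q3wk, 3k/(3k+1) for 2q3wk and 3k/(3k+2) for q1wk. The IDI does not enter this factor.

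| Cycles k | q3wk | 2q3wk | q1wk | 2q3wk minus q1wk (points) |
|---|---|---|---|---|
| 1 | 100% | 3/4 = 75.0% | 3/5 = 60.0% | 15.0 |
| 2 | 100% | 6/7 = 85.7% | 6/8 = 75.0% | 10.7 |
| 4 | 100% | 12/13 = 92.3% | 12/14 = 85.7% | 6.6 |
| 6 | 100% | 18/19 = 94.7% | 18/20 = 90.0% | 4.7 |

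At 35 cycles the factors are 99.1% (2q3wk) and 98.1% (q1wk).

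**RDI as printed.** One IDI of 2 mg/kg serves every regimen. For compliant subjects, ADI is 3.75k/(3k+2) on q1wk 1.25 mg/kg and 3k/(3k+1) on 2q3wk 1.5 mg/kg:

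- k=1: 0.75 and 0.75 mg/kg/week
- k=2: 0.938 and 0.857
- k=4: 1.071 and 0.923

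A common divisor keeps that order. At k=4, with the IDI read as 2 mg/kg per 3 weeks, printed RDI is 160.7% and 138.5%; read as 2 mg/kg per week, it is 53.6% and 46.2%. In both readings q1wk 1.25 mg/kg is level at one cycle and higher afterwards.

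**RDI with a regimen-specific IDI.** Dividing ADI by each regimen's own planned weekly intensity returns the factors in the table. The gap in the last column then appears although both groups were dosed in full.

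**Check of the fix.** Day 1 of the last LV cycle is 21(k−1) days after the first dose. Adding 21 gives 21k days, or 3k weeks, on every schedule, so compliant subjects show 100% at every k.

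**The case against.** *Scope.* The SAP describes a q3wk-only study, for which the rule is exact. This stands. The fault is that SAP 6.4 was not carried forward to Amendment 04, and SAP 1 allows amendment before database lock. The line still deserves a specific mention because 21 days matches the cycle length on every schedule and would be easy to leave unchanged.

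*Ranking.* A reader might infer that the SAP as printed will show Arm 3 (q1wk) with lower RDI than Arm 2 (2q3wk). The documents do not support that: under the common IDI the order is a tie and then the reverse. The false gap appears only when the IDI is corrected and the period is not.

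*Link to the 2q3wk rationale.* A reader might also infer that this artefact produced, or would reproduce, the fall in dose intensity described in Protocol 3.2.5. That fall was seen in SGNLVA-001, whose formula is not given here, and it developed by Cycle 2. The deficit from a fixed tail shrinks as cycles accrue. Size alone could still confuse: two of three doses is 66.7%, and a perfectly dosed q1wk subject shows 60% at one cycle and 75% at two.

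*Impact.* No endpoint, futility rule or planned test uses dose intensity. SAP 6.4 also lists number of cycles, average dose per cycle and modifications by cycle, none of which uses this period and which together would reveal full compliance. This stands and limits the severity.

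*Duration of treatment.* A flat inflation of two weeks or one week would overstate the effect, because an earlier EOT visit, death or new therapy ends the count. EOT is normally 30 to 37 days after the last dose (Protocol 6.6), so the 21-day term will often govern, but not always.

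*Limits of the fix.* For a subject whose last dose is on Day 1 of a cycle, the current and proposed periods coincide. One q1wk dose gives 33.3% and one 2q3wk dose gives 50.0% under both. This also stands.

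**Conclusion.** The point holds as a failure to update SAP 6.4 for Parts B and C. The fixed tail multiplies ADI in fully compliant subjects by 3k/(3k+2) under q1wk and 3k/(3k+1) under 2q3wk, whatever IDI is used. The loss is greatest in subjects who stop early. Printed RDI masks this behind a common 2 mg/kg IDI. That figure also disagrees with the 2.5 mg/kg in SAP 3, and the two passages must be reconciled. Making the IDI regimen-specific without changing the period would turn the masked bias into a believable but false deficit for q1wk of 15.0, 10.7, 6.6 and 4.7 points at 1, 2, 4 and 6 cycles. Duration of treatment is lengthened by up to two weeks (q1wk) or one week (2q3wk) when no earlier end date applies. These figures assume full, on-time cycles that end with the last planned dose. Only a descriptive exposure summary is affected, so the severity is minor.

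**What to change.** In SAP 6.4, for every schedule, end the ADI period at Day 1 of the last cycle in which LV was given + 21 days. Use the same date in place of last dose + 21 in duration of treatment, and keep the existing truncation at EOT visit, death or new therapy. Tie the wording to LV because pembrolizumab may continue after LV stops (Protocol 4.4.1 and 5.3.4.3). Under q1wk and 2q3wk, Day 1 can be delayed but not omitted (Protocol 5.2.4.2 and 5.2.4.3), so the anchor date exists.

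Make the change together with a schedule-specific IDI taken from each regimen's planned dose per cycle, after the sponsor has reconciled the 2 mg/kg figure with the dosing sections.

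The cost is a short wording and programming change with no new data. Site conduct does not change, so Protocol 9.3 requires no protocol amendment. Values for Part A q3wk dosing stay as they are. The downside is that a subject who stops mid-cycle is charged for that cycle's remaining planned doses; the SAP should say so.
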